3.4 Study Duration and Schedule

Patients will partake in 7 visits over a 3 month period at the dermatological department of Bispebjerg Hospital (time schedule in Section 5):

- 1 Screening visit
- 1 Treatment day
- 5 Control visits after treatment on Day 1, 5, 14, 30 and Month 3

The study is expected to run between March 2018 - March 2019

Recruitment start	1. March 2018
Treatment start	1. March 2018
Final patient treatment	1. December 2018
Final control visit	1. March 2019

3.5 Preliminary Study

In the beginning of the trial period, a preliminary study in 4-6 patients of the intended treatment will be conducted to confirm: a) uniform cisplatin and 5-FU uptake in treated BCC tumors and b) no clinically relevant systemic drug uptake. Thus, up to 6 patients will each provide a single 4 mm punch biopsy of a treated BCC and one 5 ml blood sample, both taken 24 hrs after AFL-assisted cisplatin+5-FU. Drug biodistribution imaging of tumor sections and drug quantification in blood will be performed at Copenhagen University using well-established analytical techniques. A biobank and contracts of collaboration pertaining to the exchange of anonymized data between institutions will be devised.

4. Participants

Up to 12 patients with superficial BCC and 12 patients with nodular BCC will be evaluated following AFL-assisted cisplatin+5-FU treatment. The unspecific inclusion of “up to” 12 patients reflects the explorative nature of this tolerability study. Should fewer patients per group provide adequate data on LRSs associated with the treatment (for example if all patients demonstrate severe LSRs), the inclusion of 12 patients will not be performed in order to spare them potential discomfort.

Recruitment will be performed by physicians at the dermatological department, Bispebjerg Hospital and by private practice dermatologists in the Copenhagen area. Procedures for informed consent are included in Bilag 2-4.

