4.1 Inclusion criteria

Subjects who meet all of the following criteria are eligible to participate in this study:

1. Histologically-verified, previously untreated superficial or nodular BCCs on the scalp, face, extremities or trunk
2. >18 years of age at baseline
3. Legally competent, able to give verbal and written informed consent
4. Subject in good general health, is willing to participate and can comply with protocol requirements.
5. Fitzpatrick skin phototype I-III
6. Female subjects of childbearing potential¹ must be confirmed not pregnant by a negative urine pregnancy test prior to trial treatment.

¹Female subjects are considered of childbearing potential unless they have been hysterectomized or have undergone tubal ligation or have been post-menopausal for at least one year prior to first visit.

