6.3.3 Histology

At the 3 month visit, a 4 mm punch biopsy will be taken centrally in treatment area for histological verification of tumor clearance. Biopsy tissue will undergo standard sectioning and histological evaluation by a board-certified pathologist at the Department of Pathology, Bispebjerg Hospital. If tumor residual/recurrence is confirmed, test areas will be treated according to clinical guidelines.

7. Potential Risks and Side Effects

In general, no serious or systemic side effects are assumed but will be reported to the relevant authorities if they occur. Topical 5-FU cream and AFL are used daily at Bispebjerg Hospital's dermatological clinic and are well-tolerated. Cisplatin has previously been examined in a live pig study where no systemic drug uptake or effects were observed. Any obtained information about adverse effects related to this study will be recorded systematically.

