7.4 Punch Biopsy and Blood Sampling

Prior to 4 mm biopsy local analgesic will be used to reduce pain. The biopsy may leave a punctiform scar. Needle-pricks associated with injection and blood sampling (preliminary study) are associated with discomfort. The risk of infection is low (<1%), and will be managed with antibiotics provided by the investigator.

8. Safety Considerations

Patients are followed closely in the initial 30 days after treatment and particularly in the first 14 days. Complete tumor removal is ensured through histological analysis at Month 3. In the event of inadequate treatment response at 3 months, or in the event of withdrawal, patients will receive conventional BCC treatment and follow-up according to national guidelines.

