9.2 Study populations

Treated study participants are divided into the following populations:

Per-protocol (PP) population:

Includes only patients that have completed all control visits as planned. Larger deviations such as

breach of inclusion criteria, inadequate outcome assessment or larger differences in treatment, are assessed before statistical analysis is conducted.

Intention-to-treat (ITT) population:

Includes all patients that have received treatment. In the event of missing data, the population is analyzed using the “last observation carried forward” approach to minimize bias associated with loss to follow up.

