10.4 Biobank

In the preliminary study, one 4 mm punch biopsy taken from the treated skin area and one 5ml blood sample per patient will confirm adequate local drug uptake and limited systemic permeation. Biopsies and blood samples are sent for analysis by collaborators at Copenhagen University. No extra material will be taken. Any remaining biological material will be returned to primary investigator [name], Bispebjerg Hospital at the end of the study for potential use in future investigations. The material will be handled confidentially and will not be used in other scientific studies without Videnskabsetisk Komite's permission. Prior to storage, permission will be sought from Datatilsynet as well as patients. The biobank expires September 1, 2019 whereafter the material is kept for 10 years for future research and thereafter be destroyed.

11. Ethics

No previous trials have investigated AFL-assisted cisplatin+5-FU as a topical treatment in patients. Based on our preclinical results, we expect to successfully treat study participant's BCCs. During the trial, individual participants will be followed closely by treating phycisians. In the event of side

effects, these will be managed according to guidelines by investigating physicians. In the event of an unsuccessful treatment outcome, histological assessment should detect residual tumor tissue at 3 months control—a duration which is in accordance with general guidelines for established non-surgical BCC treatments. Patients will receive conventional therapy to ensure complete tumor removal. Beyond removal of the tumor, patients are not anticipated to benefit from the study.

While cisplatin and 5-FU are chemotherapeutics, side effect profiles associated with IV therapy (i.v. doses: 100 mg/m² (cisplatin); 400-600 mg/m² (5-FU)) cannot be transferred to the topical administration route used here. We do not anticipate systemic drug exposure due to the applied ultralow drug doses and small treatment surface areas. On the other hand, notable local erythema/edema, flaking/scaling, crusting, and erosion/ulceration are anticipated and represent, in addition to the inconvenience of multiple visits to the Hospital as well as invasive biological sampling, drawbacks of study participation. Still, as with standard 4 week topical 5-FU treatment, we expect local skin reactions to be tolerable and heal without sequelae.

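### Up to 6 preliminary patients have a 4 mm punch of the treated tumor at 24 hours, and no analysis rule separates its effect from that of treatment

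*Combined protocol and SAP*

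**What the plan says.** Section 3.5 plans that "a preliminary study in 4-6 patients of the intended treatment will be conducted". Within it, "up to 6 patients will each provide a single 4 mm punch biopsy of a treated BCC", together with a blood sample, "both taken 24 hrs after AFL-assisted cisplatin+5-FU". Section 10.4 describes the same sampling as "one 4 mm punch biopsy taken from the treated skin area and one 5ml blood sample per patient". Neither section gives the position of the punch within the lesion. The schedule in section 5 lists a biopsy only at Month 3.

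Section 9.1 plans 12 superficial and 12 nodular BCCs in 24 subjects, which is one lesion per subject. In 9.2 the ITT population "Includes all patients that have received treatment". The per-protocol population requires completed control visits, with larger deviations reviewed before analysis. Neither definition mentions the preliminary patients.

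The outcomes that an early punch can reach are:
- **Primary (6.1):** LSRs in the treated area on Days 1, 5, 14 and 30, and side effects including scarring and infection up to 3 months. On biopsies, section 7.4 says: "The biopsy may leave a punctiform scar".
- **Secondary (6.2, 6.3.3):** tumor size in mm and clearance yes/no, judged clinically and by imaging, and Month 3 histology, for which "a 4 mm punch biopsy will be taken centrally in treatment area".

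**The concern.** The punch removes part of the tumor whose size and clearance are then measured. It also leaves a wound, and possibly a scar, inside the area scored for tolerability. The trial is uncontrolled, so no comparison arm carries the same effect. Read literally, the ITT rule includes these lesions unmarked, and a planned biopsy is not a deviation that the per-protocol review would catch.

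Section 8.2 does not help to separate the two sources. Reactions on the LSR scale are not reported as adverse events, and the location of an event is recorded only as inside or outside the treated area. A biopsy-site infection would therefore be logged as a treated-area event. At stake are the only efficacy signal from this trial and the attribution of harms in its primary outcome.

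**Working it through.** The planned 24 is 12 + 12. Section 9.1 says that no formal calculation was made, so there is nothing further to reproduce. The checks below size the possible effect.

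**1. Share of lesions, if the preliminary patients are among the 24.** 4/24 = 16.7% and 6/24 = 25%. If all 6 fell in one subtype, 6/12 = 50% of that group.

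**2. Tumor surface removed.** For a round tumor of diameter d mm that fully contains the punch, the share is (4/d)². The diameters are assumed: section 4.2 sets only maximum sizes (20 mm on face or scalp, 50 mm elsewhere) and no minimum.

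| d (mm) | Share removed |
|---|---|
| 4 | 100% |
| 5 | 16/25 = 64% |
| 6 | 16/36 = 44% |
| 8 | 16/64 = 25% |
| 10 | 16/100 = 16% |
| 20 | 16/400 = 4% |

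**3. Upper bound for clearance.** Let p be the true clearance rate and b the number of biopsied lesions, and suppose that every biopsied lesion is scored clear. The observed rate is ((24 − b)p + b)/24, so the inflation is (b/24)(1 − p). The documents give no clearance rate, so p is an assumption, shown over a range.

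| Assumed p | b = 6 | b = 4 |
|---|---|---|
| 50% | 0.25 × 0.5 = 12.5 points | 0.167 × 0.5 = 8.3 points |
| 70% | 7.5 points | 5.0 points |
| 80% | 5.0 points | 3.3 points |
| 90% | 2.5 points | 1.7 points |

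If the punch converted only half of the would-be failures among the biopsied lesions, each figure would halve (6.25 points at p = 50%, b = 6).

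**4. Share of the area scored for LSRs.** The treated area is the tumor plus a 5 mm margin, so d + 10 mm across. The punch covers (4/15)² = 7% of it for a 5 mm tumor and (4/20)² = 4% for a 10 mm tumor.

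**5. Timing.** A punch at 24 hours coincides with the Day 1 visit. The Day 5, 14 and 30 LSR scores are therefore taken with a healing biopsy wound in the field, and so is the Day 1 score if it is made after the punch.

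**6. Precision without the biopsied lesions.** 24 − 6 = 18 or 24 − 4 = 20 lesions remain. Interval width grows by about √(24/18) = 1.15 or √(24/20) = 1.10. At an observed 50%, the exact 95% interval is 29-71% with 12/24, 27-73% with 10/20 and 26-74% with 9/18. For a harm with zero events, the exact two-sided 95% upper limit is 14.2% with n = 24 and 18.5% with n = 18, which is 18.5/14.2 = 1.30 times as high.

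**The case against.** - **Membership is not stated.** Section 3.5 is called a preliminary study, has its own aims (drug uptake and systemic exposure) and precedes the section on participants. The schedule shows no 24-hour biopsy. If these patients are additional to the 24 and contribute only uptake data, the problem disappears. This stands as a limit on the point. But the plan does not say so, the patients receive the intended treatment, and the ITT wording takes in every treated patient.
- **Partial removal is not clearance.** Clinical examination, dermoscopy and imaging cover the whole lesion, so residual tumor can still be found in all but very small lesions. Only a tumor of about 4 mm or less, fully covered and within the depth of the punch, could be removed by the punch alone. This stands, and it is why the figures in step 3 are ceilings. Resampling of the early site at Month 3 is possible but cannot be shown, because the early position is not given.
- **The tolerability effect is modest.** The punch covers a few percent of the treated area, section 7.2 already expects erythema in 94-100% and scabbing in 50-95%, and an unblinded physician may recognize the biopsy scar. This stands for incidence. It does not fully answer the point, because LSR severity and duration are also outcomes and nothing requires the biopsy site to be recorded apart.
- **A reader might infer a further problem from the diagnostic biopsy.** Entry requires "Histologically-verified, previously untreated superficial or nodular BCCs", so a tumor already removed at diagnosis might seem able to count as cleared. The documents do not support this reading. Section 5.2.1 has the tumor delineated clinically and by imaging on Day 0, builds the treatment area around it and documents its baseline size.

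**Conclusion.** The concern holds in a limited form. As written, the plan allows tissue removal and a biopsy wound or scar to be counted as treatment results, and it leaves open whether the affected patients belong to the 24. If they do, 17-25% of lesions are affected. The clearance rate could be inflated by at most 12.5 points (6 biopsied, assumed true rate 50%), falling to 2.5 points at 90%; with 4 biopsied the ceiling runs from 8.3 to 1.7 points. These ceilings need every biopsied lesion to be scored clear. The realistic effect depends on tumor size and is small for large tumors.

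Two stronger readings are not supported. One is that clearance will in fact move from 50% to 62.5% (9/18 to 15/24): the 50% is assumed, and no tumor-size data suggest that all 6 lesions would clear. The other is that scarring will read 6/24 (25%): that needs every punch to scar and every such scar to be attributed to treatment. What can be said is that both outcomes are open to this effect and that the plan has no means of separating it.

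**What to change.** In 9.2 and 9.3:
1. State whether the 4-6 preliminary patients are among the 24 or additional to them.
2. Base the main analysis of tumor size and clearance, including Month 3 histology, on lesions without the 24-hour biopsy, and report the biopsied lesions separately.
3. Keep all treated patients in the tolerability analysis. Record scar, infection and reaction at the biopsy site separately from the rest of the treated area, and show scarring and post-Day 1 LSRs with and without the biopsied lesions.

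The 24-hour biopsy should also be added to the schedule in section 5, and its position recorded so that the Month 3 histology can be interpreted.

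The cost is 18-20 instead of 24 lesions in the main clearance analysis, with intervals about 10-15% wider, and a little more recording. Removing these patients from the tolerability analysis altogether would be a poorer trade, because with no events the upper limit for a harm would rise from 14.2% to 18.5%. Showing both versions avoids that loss.

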3.3 Intervention Summary

For a detailed description of interventions, please see Section 5.

Patients will receive AFL-assisted cisplatin+5-FU as a treatment for their BCC. In brief, treatment areas consisting of tumors and a 5 mm margin will undergo AFL exposure (Ultrapulse DeepFx CO₂ laser, Lumenis, Santa Clara, CA, USA) followed by 60 min topical application of a marketed and commercially available IV cisplatin solution (0.1% Accord Healthcare Limited A/S) at a dose of 0.25 ml per cm². After removal of cisplatin, a commercially distributed 5-FU cream (5% Efudix®, Meda Pharmaceuticals A/S) will be applied to the treatment area at a dose of 0.125 ml per cm² and left under occlusion. After skin evaluations on Day 1 and 5 after treatment, the same 5-FU dose will be applied, again left under occlusion. In total, 5-FU will remain on the skin for 7 days after AFL treatment whereafter it will be washed off.

An additional repeat AFL-cisplatin+5-FU treatment on Day 30 will be offered if tumors persist, based on clinical evaluation and imaging on Day 30.

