5.2.3 Topical Cisplatin

After AFL exposure, a well consisting of a customized hydroactive bandage (DuoDerm Hydroactive™, ConvaTec, Flintshire, UK) is applied to the test area, defined as the BCC and 5 mm margin, and sealed shut with transparent dermatological film (TegaDerm® film dressing, 3M Medical, MN, USA). Cisplatin solution 0.1% (Accord Healthcare Limited A/S) is applied through the transparent film using a blunt-tipped syringe, ensuring spatial containment of the solution with no loss to the environment. The amount of solution will fill the well to ensure coverage of the entire skin surface. Accordingly, up to 0.25 ml per cm² (0.25 mg) will be applied depending on tumor delineation. Cisplatin is left on the skin for 60 minutes, whereafter the solution is removed by light suction using a blunt-tipped syringe. After drug removal, all materials will be disposed of according to guidelines for materials contaminated with cytotoxic-agents.

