5.2.4 Topical 5-Fluorouracil (5-FU)

After cisplatin removal, the well bandage is disposed of and a thick amount of Efudix® 5% 5-FU cream (Meda Pharmaceuticals A/S, UK) is applied to the entire test area (corresponding to up to 0.125 ml per cm² skin). After 5-FU application, transparent dermatological film (TegaDerm® film dressing, 3M Medical, MN, USA) is applied to the test area as an occlusive dressing. The cream is left on the skin until next control visit. Thus, on Day 1 and 5, Efudix cream is reapplied at the same dose. The cream is removed on Day 7 after AFL treatment.

STUDY SET UP	Visit 1 Screening	Visit 2 Treatment Day 0	Visit 3 Day 1	Visit 4 Day 5 +/- 2 days	Visit 5 Day 14 +/- 3 days	Visit 6 Treatment* Day 30 +/- 5 days	Visit 7 Month 3 +/- 5 days
Screening & enrolment							
Informed consent	✓						
Inclusion/exclusion criteria	✓						
Relevant medical history	✓						
Location of BCC	✓						
Pregnancy test when relevant		✓				✓	
Interventions							
AFL		✓				(✓)	
Apply topical cisplatin(60min)		✓				(✓)	
Apply 5-FU under occlusion		✓	✓	✓		(✓)	
Clinical LSR evaluation							
FDA-approved LSR scale		✓	✓	✓	✓	✓	
Clinical photos		✓	✓	✓	✓	✓	
Safety							
Clinical evaluation		✓	✓	✓	✓	✓	
Tumor size and clearance evaluation							
Clinical/dermoscopic photos		✓	✓	✓	✓	✓	
D-OCT		✓				(✓)	
RCM		✓					
HIFU		✓				(✓)	
Biopsy							✓

*Offered if BCC residual or recurrence; (✓): Treatment/technique can be relevantly applied if tumor residuals are identified clinically or by D-OCT/RCM and there is no crusting etc. LSR: Local skin reactions, RCM: Reflectance confocal microscopy, D-OCT: Dynamic optical coherence tomography

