9.1 Sample size

The primary objective of this explorative trial is to investigate tolerability of AFL-assisted cisplatin+5-FU to ensure that intolerable/severe or serious related adverse events remain minimal for the observed efficacy. While no formal statistical calculation has been performed, 12 superficial and 12 nodular BCCs in 24 subjects are considered sufficient to estimate benefit/risk of the treatment.

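### The protocol does not reconcile the 24-hour punch biopsy and only blood sample in the preliminary patients with the occluded 5-FU reapplied to the same area from Day 1 to Day 7

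*Combined protocol and SAP*

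**What the plan says.** Section 3.5 describes "a preliminary study in 4-6 patients of the intended treatment will be conducted to confirm" uniform drug uptake in the tumour and no clinically relevant systemic uptake. Up to 6 patients each give "a single 4 mm punch biopsy of a treated BCC and one 5 ml blood sample, both taken 24 hrs after AFL-assisted cisplatin+5-FU". Section 10.4 repeats the count: "one 4 mm punch biopsy taken from the treated skin area and one 5ml blood sample per patient". No other blood draw is planned.

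The treatment sections set the 5-FU course. Section 3.3: "After skin evaluations on Day 1 and 5 after treatment, the same 5-FU dose will be applied, again left under occlusion". Section 5.2.4: "Thus, on Day 1 and 5, Efudix cream is reapplied at the same dose", with removal on Day 7. The cream "is applied to the entire test area (corresponding to up to 0.125 ml per cm² skin"). Section 5.2.3 fixes that area when it describes the cisplatin well, which "is applied to the test area, defined as the BCC and 5 mm margin".

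The schedule table after Section 5.2.4 ticks 5-FU at Visit 3 (Day 1) and Visit 4 (Day 5). Its biopsy row is ticked only at Month 3, and it has no row for the 24-hour biopsy or the blood sample. Section 7.4 covers biopsy pain, scarring and infection and does not mention the cream. Section 7.2 relies on the preliminary study to reassess the expectation of negligible systemic exposure.

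**The concern.** Two procedures fall on the same lesion at the same visit, and no section says how they fit together. Three things depend on the answer.

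- **Safety wording.** If the stated rules are simply followed, a cytotoxic cream lies under occlusion over a recent biopsy site, and the risk section does not discuss it.
- **The uptake conclusion.** The blood sample is timed with the biopsy, so it cannot inform on uptake after the punch. It probably also precedes most of the 5-FU course.
- **The primary outcome.** Local skin reactions, infection and scarring are the primary tolerability measures (Sections 3.4 and 6.1), and Section 7.4 itself lists scarring and infection as risks of a punch. In a biopsied patient such an event may come from the biopsy rather than the treatment.

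The opposite assumption also leaves a gap. If the cream were withheld after the punch, these patients would receive 1 of 3 applications. That is not the intended treatment named in Section 3.5, and it could count as a larger treatment difference under the per-protocol definition in Section 9.2.

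**Working it through.** **Timing.** The punch and blood sample are at 24 hours, which is Day 1. 5-FU is applied on Days 0, 1 and 5 and removed on Day 7.
- Cream over the punch site: Day 7 − Day 1 = 6 days.
- Applications after the sample, if blood is drawn before the Day 1 cream: 2 of 3. The sample then covers 1 of 3 applications and 1 of 7 days of exposure.
- The order of steps within the visit is not written. In either order no later sample is planned.

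**Place.** The cream covers the entire test area, which is the BCC plus 5 mm. A punch of the BCC lies inside it.

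**Dose per area, checked against the plan.** Inputs are 0.125 ml/cm² (Sections 3.3 and 5.2.4), 5% cream at 50 mg/g (background section), and an assumed density of 1 g/ml.
- 0.125 × 50 = 6.25 mg/cm², which matches the background section.
- For a density of 0.9 to 1.1 g/ml the range is 5.6 to 6.9 mg/cm².

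**Amount over the punch site.**
- Punch area: π × 0.2² = 0.126 cm².
- 5-FU over it: 0.126 × 6.25 = 0.79 mg per application, or 1.57 mg for Days 1 and 5 together.
- Intravenous dose in the protocol: 400–600 mg/m². With an assumed body surface of 1.5–2.0 m², this is 600–1,200 mg.
- If everything over the site were absorbed: 1.57/1,200 = 0.13% to 1.57/600 = 0.26% of one intravenous dose.

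**Punch compared with the laser-opened surface.** Assume a circular lesion of diameter d mm and the maximum 10% density (Section 5.2.2). The treated area is π × ((d + 10)/20)² cm², and the opened surface is 10% of it. Because 10% of the punched skin is already ablated, the net addition is 0.9 × 0.126 = 0.113 cm². The 20 mm and 50 mm sizes are the limits in Section 4.2 (face or scalp, and elsewhere); 5 mm and 10 mm are illustrative.

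| Lesion (mm) | Treated area (cm²) | Laser-opened (cm²) | Net addition by punch |
|---|---|---|---|
| 5 | 1.77 | 0.177 | 64% |
| 10 | 3.14 | 0.314 | 36% |
| 20 | 7.07 | 0.707 | 16% |
| 50 | 28.27 | 2.827 | 4% |

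A lower density would raise these shares. They compare surface area only; they ignore depth and the walls of the laser channels, and the documents give no link from opened surface to uptake.

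**Patients affected.** 4 to 6. If they count among the 24, that is 4/24 = 17% to 6/24 = 25%. The protocol does not say whether they do.

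**The case against.** The strongest reply is that the protocol is silent rather than wrong. Section 3.5 never says that biopsied patients receive the Day 1 and Day 5 cream, and the schedule table does not list the preliminary procedures at all. A reader might infer that the plan directs 5-FU onto a fresh, open, full-thickness wound after the blood has been drawn. The documents do not support that: they give neither the depth of the wound, nor whether it is closed, nor the order of steps. This part of the reply stands, and the point is accordingly about unreconciled sections.

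A reader might also infer a systemic hazard from the extra opened surface. That is not supported either. The addition shrinks quickly with lesion size, and the amount of drug over the site is well under 1% of an intravenous dose even if all of it were absorbed. Nor are these patients alone in having 5-FU on breached skin. The laser breaches the barrier in everyone, and Section 7.2 expects erosion in 50–95%. The punch differs in cause and form.

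Two further replies stand in part. A single 24-hour sample precedes the later applications with or without a biopsy, so that limit is not caused by the punch, but the uptake conclusion still has to respect it. Infection management (Section 7.4) and adverse event recording with location and drug association (Section 8.2) also exist, so biopsy risk is not ignored; only drug contact with the site is. However, Section 8.2 records reactions on the grading scale as local skin reactions and not as adverse events, and nothing there marks a patient as biopsied.

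Finally, the trial is exploratory ("While no formal statistical calculation has been performed", Section 9.1), and no bias in the tolerability results can be quantified. That is true, and it argues for separate reporting rather than a change of design.

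**Conclusion.** The point holds as an unreconciled overlap, of minor to moderate severity. Followed literally, Sections 3.3, 3.5 and 5.2.4 put occluded 5-FU over a biopsy site for about 6 days in up to 6 patients. They also leave the only blood sample covering 1 of 3 applications if it is drawn before the Day 1 cream.

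This rests on three readings: that biopsied patients complete the 5-FU course, which the reference to the intended treatment and the absence of any exemption suggest but do not state; that blood is drawn before the new cream; and that the cream density is about 1 g/ml. Effects on the primary tolerability summary arise only if these patients count in the cohort.

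The documents show a risk that is not addressed and an uptake conclusion that could be read too widely. They do not show harm, and they contain no data on uptake through a punch site.

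**What to change.** 1. Before the first preliminary patient, reconcile Section 3.5 with Sections 3.3 and 5.2.4 and the schedule table. State what happens to the Day 1 and Day 5 applications in a punched lesion and the order of steps at the Day 1 visit, and add rows for the 24-hour biopsy and blood sample. The clinical rule is for the sponsor to decide. Reflect the resulting risk in Section 7.4.
2. Limit the conclusion on systemic uptake to the first 24 hours, before the Day 1 and Day 5 applications and before any punch.
3. Flag the biopsied patients in the data and report their local skin reactions, infection and scarring after Day 1 separately. State whether they count in the cohort; if they do, show the primary tolerability summary with and without them.

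The cost is a few sentences, two table rows and one data flag, with no extra visit, sample or patient. The price in information is 4 to 6 fewer patients in the unbiopsied summary and a narrower uptake conclusion.
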